1 SPECIFIC AIMS

Upper gastrointestinal symptoms (early satiety, pain, nausea, and vomiting) are not uncommon in diabetes mellitus (DM)¹. These symptoms are often attributed to delayed gastric emptying or gastroparesis. Over a 10-year time period, the risk of developing gastroparesis was 5% in type 1 DM (HR 33, 95% CI 4.0, 274 adjusted for age and gender versus controls), 1% in type 2 DM (HR 7.5 (95% CI: 0.8, 68) adjusted for age and gender versus controls and 1% in controls². However, similar to functional dyspepsia³, the precise contribution of abnormal gastric emptying to symptoms in patients with DM gastroparesis is unclear. Indeed, a majority of patients with DM and delayed gastric emptying are asymptomatic. In our cohort of DM patients with GI symptoms who underwent scintigraphy, a substantial proportion, i.e., 55 of 129 patients (42%) had normal gastric emptying; the remainder had had delayed (36%) or rapid GE (22%)⁴. Moreover, symptoms did not predict abnormal (i.e., delayed or rapid) gastric emptying. Other, small, studies reported impaired gastric accommodation and increased gastric sensation in DM^{5,6} but did not describe the relationship of these abnormalities to upper GI symptoms.

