A recent study suggests that patients with functional dyspepsia have low-grade mucosal inflammation, abnormalities of cell-to-cell adhesion proteins which predispose to increased epithelial permeability, and a leaky epithelial barrier¹⁶. Type 1 DM is associated with increased small intestinal permeability even in subjects who do not have celiac disease^{17,18}. Moreover, a comparison of 339 type 1 DM patients and 89 first degree relatives observed higher serum zonulin levels in type 1 DM patients than controls or relatives; patients with increased zonulin had increased epithelial permeability¹⁹. The only study which evaluated small intestinal permeability in type 2 DM used suboptimal techniques and reported normal permeability²⁰.

Our *overall hypothesis* is that intestinal chemosensitivity related to increased epithelial permeability and CCK explains symptom severity in patients with DM with upper GI symptoms.

The **specific aims** of this study are to address the following hypotheses in 24 healthy subjects, 40 patients with DM and GI symptoms, and 40 patients with functional dyspepsia:

- 1) **A) Patients with DM and GI symptoms have increased intestinal chemosensitivity compared to controls and B) Intestinal chemosensitivity predicts severity of ongoing upper gastrointestinal symptoms independent of gastric emptying.** Intestinal chemosensitivity will be recorded by evaluating symptoms during duodenal lipid infusion (222 kcal, 222 ml) and placebo or the GLP-1 receptor antagonist exendin 9-39 over 2 hours; plasma hormones (i.e., glucose, CCK, GLP-1, PYY, C-peptide, will also be measured. Delivering nutrients into the duodenum will ensure that hormonal responses are not affected by gastric emptying disturbances. Day-to-day symptoms will be evaluated by the Nepean dyspepsia severity index and the GCSI. The relationship between daily symptoms and intestinal chemosensitivity will be assessed in a model which also incorporates gastric emptying and accommodation.

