3.2 Study Subjects

We plan to accrue up to 115 subjects to ensure that 104 subjects complete the study in its entirety. 40 patients with DM and GI symptoms and 40 patients with functional dyspepsia will be recruited from the clinical practice; 24 healthy subjects will be recruited by public advertisement. To reduce the possibility of demographic differences between controls and patients, we will "frequency match" on age and gender by recruiting 5 controls after each set of 5 patients is studied. Doing so will provide similar age and gender distribution in each type. We will also attempt to recruit an even number of subjects with type 1 and 2 DM.

Inclusion criteria for controls

1. Healthy male or non-pregnant, non-breastfeeding female volunteers;
2. 18-70 years old;
3. Able to provide written informed consent before participating in the study;
4. Able to communicate adequately with the investigator and to comply with the requirements for the entire study

Additional inclusion criteria for patients

1. Symptoms of dyspepsia (i.e., early satiety, postprandial discomfort, nausea, vomiting, regurgitation)

2. Patients in the DM group will also require Type 1 or 2 DM of \geq 3 years duration; in patients with type 2 DM, the dyspepsia symptoms should have begun or worsened after DM was diagnosed

Exclusion criteria – for patients and controls

1. Major abdominal surgery (i.e., appendectomy, cholecystectomy, tubal ligation, hysterectomy, and limited colonic resection are permissible)
2. Clinical evidence (including physical exam and EKG) of significant cardiovascular, respiratory, renal, hepatic, gastrointestinal, hematological, neurological, psychiatric or other disease that may interfere with the objectives of the study and/or pose safety concerns
3. Opiates, alpha adrenergic agonists, metoclopramide, and high doses of anticholinergic agents (eg, amitriptyline greater than 50 mg daily). If medically safe, these drugs may be discontinued for four half lives prior to study assessments
4. Treatment with GLP-1 agonists and amlodipine which cause vagal blockade and may affect central processing of pain
5. Use of tobacco products within the past 1 week or NSAIDs or aspirin within the past week (since they all may affect intestinal permeability)
6. Bleeding or clotting disorders or medications that increase risk of bleeding from mucosal biopsies
7. Positive tissue transglutaminase antibodies (TTG),

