8. For two days prior to studies, subjects will be instructed to avoid ingestion of artificial sweeteners such as SplendaTM (sucralose), NutrasweetTM (aspartame), foods containing lactulose or mannitol
9. Pregnant or breast-feeding females
10. Known intolerance or allergy to eggs
11. Poor peripheral venous access, if central venous access is not available
12. Any other condition or prior therapy that, in the opinion of the investigator, would make the patient unsuitable for the study

Exclusion criteria for controls only

1. Current symptoms of a functional gastrointestinal disorder assessed by questionnaire

Exclusion criteria for patients only

1. Severe vomiting that would preclude tube placement or participation in the study
2. Structural cause for symptoms by endoscopy within the past 48 months
3. Patients with gastric pacemakers

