3.5 Data Analysis

Chemosensitivity will be measured using a 100mmVAS anchored at each end (left end:No symptoms, right end: Severe symptoms). The distribution of this measure will be checked for its approximation to a gaussian distribution. An analysis to provide preliminary data for a new grant submission will be examined after approximately 15 subjects (5 DM, 10 controls) have completed the studies, but there is no intention of stopping the study based on the preliminary results. We anticipate conducting this analysis in July 2014 or thereafter.

Question	Summary Parameter	Statistical analysis
Sensation (symptoms) during enteral infusion (Aim 1)	VAS score	i) compare VAS scores in response to lipid infusion + exendin vs. lipid infusion + placebo separately for each group using a 2-sample t-test or Wilcoxon rank sum test ii) compare the delta VAS scores (exendin – placebo) to assess the association with subject status (FD,DM, and controls) using an ANOVA model (adjusting for covariates, eg, type of DM) or Kruskal-Wallis test.
Relationship between intestinal chemosensitivity and severity of ongoing upper GI symptoms	Mean symptom score and QoL defined by the Nepean dyspepsia index and GCSI diary	Multiple linear regression with the dependent variable = mean symptom score, and separately the QoL score (possibly after rank transformation). Potential predictor variables = VAS score during enteral lipid + placebo infusion, gastric emptying, age, gender, BMI
Relationship between sensation and plasma hormones during lipid infusion (Aim 2)	Using the VAS score from the enteral infusions and for hormones, the AUC values	Spearman correlations between the VAS score and the AUC values for the various hormones, overall and separately by group (FD,DM, controls)
Small intestinal tight junction proteins,	Protein expression, lactulose:mannitol	Assess the associations between permeability and protein expression, vs. the VAS score, based on Spearman

permeability, intestinal chemosensitivity	ratio, VAS score	correlations.
---	------------------	---------------

The sample size estimate is based on our previous study which evaluated intestinal chemosensitivity in functional dyspepsia in which the proportions with severe symptoms were assessed. [In the current proposal, symptoms during lipid infusion will be evaluated on a continuous VAS scale, likely providing the ability to detect smaller effect sizes]. The effect of lipid plus

Group	Proportions (%) with severe symptoms			

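### The Aim 1B regression has no FD/DM/control term and no stated population, so its VAS coefficient can reflect how the groups were recruited rather than a relation among patients

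*Combined protocol and SAP*

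**What the plan says.** Aim 1B states that "Intestinal chemosensitivity predicts severity of ongoing upper gastrointestinal symptoms independent of gastric emptying" (Section 1). The matching row of the Section 3.5 table specifies "Multiple linear regression with the dependent variable = mean symptom score, and separately the QoL score (possibly after rank transformation". Its covariate list reads: "Potential predictor variables = VAS score during enteral lipid + placebo infusion, gastric emptying, age, gender, BMI". The row contains no term for FD, DM or control, does not ask for results within group, and does not name the subjects to be analysed.

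Three other places bear on this:

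- Section 1 introduces the aims as work to "address the following hypotheses in 24 healthy subjects, 40 patients with DM and GI symptoms, and 40 patients with functional dyspepsia".
- Section 3.2 recruits on symptoms. Controls are excluded for "Current symptoms of a functional gastrointestinal disorder assessed by questionnaire", while patients must have "Symptoms of dyspepsia (i.e., early satiety, postprandial discomfort, nausea, vomiting, regurgitation".
- Two other rows of the same table do deal with group. The first tests subject status and allows for type of DM. The hormone row asks for correlations both pooled and within each of the three groups.

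**The concern.** The dependent variable is ongoing symptom severity, and Section 3.2 uses symptoms to decide who is a control and who is a patient. Group is therefore a strong determinant of the outcome by design. Group is also expected to be related to the main predictor. Aim 1A predicts higher chemosensitivity in DM, and the Figure 1 legend in Section 2 reports that more FD patients than controls had at least moderate symptoms during lipid infusion. A variable related to both sides of a regression and left out of it is a confounder.

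At stake is the meaning of the Aim 1B result. A significant VAS coefficient should show that a more chemosensitive patient has worse daily symptoms. Without a group term, it could show only that patients differ from asymptomatic controls on both measures. The patient-control difference in VAS is already the subject of Aim 1A.

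**Working it through.** The plan gives no sample size, power or effect size for this regression, so there is no stated figure to reproduce. The check asks how often the listed model declares VAS significant when VAS and symptoms are unrelated inside every group.

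**Usable sample.** The predictor is the VAS during lipid plus placebo, and randomisation is 1:1 within group. The sample-size table in Section 3.5 gives 12 controls, 20 FD and 20 DM in that arm: 12 + 20 + 20 = 52, of whom 40 are patients.

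**Expected artefact.** Let patients exceed controls by d SD on VAS and g SD on symptoms, with within-group SD 1 and no within-group relation. The expected pooled slope is approximately

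b = p(1 − p)·d·g / (1 + p(1 − p)·d²), where p = 40/52.

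Here p(1 − p) = (40 × 12)/52² = 480/2704 = 0.178. For d = 1 and g = 3, b = 0.533/1.178 = 0.45 (0.47 in simulation). For d = 0.5 and g = 2, b = 0.178/1.044 = 0.17 (0.17 in simulation). The true within-group slope is zero in both cases.

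**False-positive rate, pooled model without group.** 4,000 simulated trials per cell; covariates unrelated to outcome; two-sided test at 0.05. The gaps are assumptions because the documents give no SDs.

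| VAS gap (SD) | Symptom gap 1 SD | 2 SD | 3 SD |
|---|---|---|---|
| 0 | about 5% | about 5% | about 5% |
| 0.3 | 7% | 8% | 10% |
| 0.5 | 8% | 14% | 20% |
| 0.8 | 14% | 30% | 42% |
| 1.0 | 18% | 43% | 60% |

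The optional rank transformation of the outcome does not cure this: at a 1.0 SD VAS gap the rates are 18%, 39% and 50%.

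**Patients only, no FD/DM term (n = 40).** If FD and DM are alike on both measures, the rate is about 5%. If they differ by 0.5 SD on both, it is 6%. At 0.5 SD on VAS and 1 SD on symptoms it is 9%, and at 1 SD on both it is 22%.

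**With group handled.** Adding group terms to the 52-subject model, or fitting the 40 patients with an FD/DM term, gives 4.2% to 5.4% in every scenario in the table. With the FD/DM term, the differing-patient-group scenarios also fall back to about 5%.

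**The case against.** The strongest reply is that the row never says controls are included. Its question is about severity of ongoing symptoms, and the abstract's overall hypothesis concerns patients with FD and with DM. A reader might infer from Section 1 that pooling is settled. It is not: pooling is the natural reading because the aims cover all three groups and the row states no restriction, but it remains an inference. If the team meant patients only, the control artefact goes, and what is left depends on how far FD and DM differ.

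The size is also assumed. Figure 1 gives a direction for FD only, and Section 1 calls the role of chemosensitivity in DM symptoms unknown. The control exclusion sets no ceiling on the Nepean or GCSI score. At a 0.3 SD VAS gap the rate is only 7% to 10%. The sample-size table even shows 68% of controls with severe symptoms on placebo, against 50% of patients. However, those are differences detectable at each sample size, not forecasts, so they do not argue against a higher VAS in patients. All of this limits the size of the problem but not its existence, since the term is absent on either reading.

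A second inference is tempting: that gastric emptying enters as one linear term and so fails to adjust for emptying that is abnormal in both directions. The documents do not support this. The row names gastric emptying among potential predictors without giving its coding. Sections 1 and 2 report that symptoms did not predict abnormal emptying in the earlier DM cohort. No passage links emptying to the VAS recorded during infusion directly into the duodenum. With weak assumed correlations (0.1 to 0.3), even a linear term gives only about 5% to 8% false positives.

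**Conclusion.** The concern holds for the missing group term. As listed, the Aim 1B model confounds VAS with group if controls are pooled, and with FD/DM status if they are not. Under no within-group relation, the false-positive rate for VAS is about 7% to 60% on the pooled reading (VAS gap 0.3 to 1.0 SD, symptom gap 1 to 3 SD). In patients only it is 6% to 22%, if FD and DM differ by 0.5 to 1 SD on both measures. It stays at 5% if the groups do not differ on VAS. All gaps are assumptions, and the inclusion of controls is inferred. The point does not extend to the handling of gastric emptying, whose coding is merely unspecified. Nor does it show that controls must be dropped, because keeping all 52 with group terms works equally well. The change should be made: the bias is avoidable and two neighbouring rows already allow for group.

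**What to change.** State the population of the Aim 1B regression and do one of the following:

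- Keep all three groups and add group terms (FD, DM, control). This costs two degrees of freedom.
- Fit the model in FD and DM patients only, with an FD/DM term, and show controls descriptively. This costs one degree of freedom, and the 12 placebo-arm controls leave this one model.

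Apply the same choice to the QoL outcome, and base the Aim 1B conclusion on that model. This changes the wording of the analysis only; no subjects, visits or measurements are added.

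As a minor note, state how gastric emptying is coded. Delayed/normal/rapid categories would suit a protocol that regards both directions as abnormal.

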Hence, we propose to evaluate the overall hypothesis that intestinal chemosensitivity related to increased epithelial permeability and GLP-1 explains symptom severity in patients with functional dyspepsia and in patients with DM and dyspepsia. 24 healthy subjects, 40 patients with DM and GI symptoms, and 40 patients with functional dyspepsia will undergo assessment of intestinal chemosensitivity during duodenal nutrient perfusion, gastric emptying (by scintigraphy), cardiovascular and GI vagal functions (plasma pancreatic polypeptide response to sham feeding and a comprehensive autonomic reflex screen), in vivo assessment of small intestinal permeability (urinary lactulose:mannitol ratio), and upper endoscopy with assessment of epithelial tight junction proteins and permeability on small bowel biopsies. During the nutrient infusion, subjects in each group (ie, healthy subjects, functional dyspepsia and DM) will be randomized to lipid infusion and placebo or lipid infusion {66.7 mL Microlipid (0.5 gm/mL diluted in water to 222 mL)} and exendin 9-39 in the ratio of 1:1. Hormonal responses (i.e., GLP-1, CCK, GIP, glucagon, PYY, C-peptide, and insulin) and plasma glucose will also be evaluated during enteral nutrient infusion. GI symptoms during each perturbation (meal, nutrient infusion) will be evaluated by validated questionnaires. Blood will be collected for DNA-based genetic analyses, initially to assess the relationship of GI sensorimotor dysfunctions and symptoms with SNPs affecting CCK and GLP-1 receptors. The analysis will assess for disturbances in these parameters in functional and DM dyspepsia, investigate associations between symptoms during enteral infusion and hormonal-epithelial functions, and evaluate relationships between daily symptoms and results of testing.

Table of Contents

ABSTRACT.....	1
1 SPECIFIC AIMS	3
2 BACKGROUND AND SIGNIFICANCE.....	5
3 RESEARCH DESIGN AND METHODS.....	7
3.1 Study Design.....	7
3.2 Study Subjects.....	7
3.3 Details of Study Assessments	8
3.4 Gene and Epigenetic Studies	15
3.5 Data Analysis	16
3.6 Potential Pitfalls.....	17
4 HUMAN SUBJECTS	17
5 SAFETY AND ADVERSE EVENTS	19
5.1 Definitions.....	19
5.2 Recording of Adverse Events	21
5.3 Reporting of Serious Adverse Events and Unanticipated Problems.....	22
5.3.1 Sponsor-Investigator reporting: notifying the Mayo IRB.....	22
5.3.2 Sponsor-Investigator reporting: Notifying the FDA.....	22
5.4 Stopping Rules	23
5.5. Medical Monitoring	23
APPENDIX.....	23

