- 2) **Intestinal chemosensitivity will be A) associated with higher plasma CCK and GLP-1 concentrations B) reduced by the GLP-1 antagonist exendin 9-39 and C) inversely associated with impaired abdominal vagal function.** This hypothesis will be evaluated by comparing intestinal chemosensitivity (a) with plasma CCK and GLP-1 concentrations (b) with and without exendin 9-39 and (c) in patients with and without and GI vagal dysfunction as assessed by the plasma pancreatic polypeptide response to sham feeding.
- 3) **A) Patients with DM and GI symptoms have abnormal epithelial tight junction proteins which predispose to increased epithelial permeability and increased small bowel permeability and B) These structural and functional markers of epithelial permeability are associated with intestinal chemosensitivity.** Intestinal permeability will be measured in vivo by two sugar urine excretion after oral ingestion. Biopsies from the distal second or third portion of the duodenum will be obtained endoscopically, to measure various markers of epithelial structure and function.

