v) Hormonal responses and symptoms during duodenal infusions. A small bore nasogastric tube will be inserted through the nostril into the stomach over a guidewire and advanced under fluoroscopic guidance until the infusion ports are in the 2nd part of the duodenum.

Thereafter, subjects in each group (ie, functional dyspepsia and DM) will be randomized to lipid infusion {66.7 mL Microlipid (0.5 gm/mL diluted in water to 222 ml)} together with placebo or exendin 9-39 in the ratio of 1:1. Lipids will be delivered into the duodenum at an infusion rate which matches the rate at which glucose enters the systemic circulation after oral glucose. After placement of an IV in the hand or forearm vein for blood draws, this hand will be placed in a hotbox heated to 55°C. We have considerable preliminary data for symptoms and hormonal responses with this paradigm. Plasma glucose, insulin, C-peptide, GLP-1, CCK, ghrelin, and PYY will be collected at 5 minute intervals for 30 minutes, 10 minute intervals from 30 – 60 minutes, and at 15 minute intervals from 60 – 180 minutes (18 times including 0 minutes).

vi) GLP-1 antagonist exendin 9-39 will be sourced from C.S. Bio, reconstituted in the Mayo Pharmacy by an established process used in previous studies, and undergo endotoxin testing, sterility testing and bacterial testing, and held in quarantine before it will be used in humans. Research compounded sterile preparations (CSP) are prepared and assessed for end preparation testing according to USP <797> in the hospital pharmacy services production lab. Each batch is tested for sterility according to USP <71> utilizing membrane filtration. The sterility testing is validated by a formulation Bacteriostasis Fungistasis test. The amount of each batch tested is determined by USP <71>. Each batch is tested for endotoxin according to USP <85>. High risk CSP are quarantined for 14 days and when all end preparation testing is completed.

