Exendin 9-39 will be administered intravenously at the same dose (1,200 pmol/kg bolus followed by infusion at 300 pmol/kg/min) as previously described at Mayo Clinic (Dr. [name])^{39, 40}. This dose has previously been shown to block the effects of GLP-1 infused at supraphysiologic doses and the effects of endogenous GLP-1 on gastrointestinal motility and insulin secretion⁴¹⁻⁴³. The effects of this dose are qualitatively similar to studies using 2.5- to 3.0-fold higher infusion rates⁴⁴⁻⁴⁶. It is possible that endogenous GLP-1 still contributes to insulin secretion in the presence of exendin-9,39; however the residual effect is likely to be small⁴⁵. For example, the 25% increase in integrated glucose concentrations with an infusion of 900 pmol/kg/min⁴⁶ is comparable to the change in glucose concentrations in other studies⁴⁰. The half life of exendin 9-39 is 33 minutes. Exendin 9-39 is very safe and well tolerated and the increase in blood glucose concentration with exendin 9-39 infusion is modest. For example, in 1 study blood glucose concentrations after a duodenal meal were on average only 6 mg/dl higher in healthy subjects and 19 mg/dl higher in T2DM for exendin 9-39 versus saline⁴⁷. Even in type 1DM, the effects of exendin 9-39 on blood glucose are modest⁴⁸. [Blood glucose data was provided as AUC rather than mg/dl]. We will monitor blood glucose by fingerstick and administer insulin as necessary (Section 3.3).

vii) Upper GI Endoscopy and Biopsies. Upper GI endoscopy will be performed in the endoscopy lab of Clinical Research Unit, Charlton 7. Patients will receive conscious sedation as required for the procedure to be conducted with comfort. A full endoscopy report will be placed in the medical record. There are 3 changes in this revision (6/15/15). Because electron microscopy studies suggest that duodenal epithelial integrity is impaired in diabetes, we propose to (i) assess mucosal impedance during endoscopy and (ii) assess routine histology with mucosal biopsies. Also, as explained below, we propose to evaluate the mucosal microbiome with biopsies

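### The Aim 2 correlations of symptom VAS with hormone AUCs ignore the randomised arm, which can cost power for CCK and GLP-1 and can distort results for analytes that exendin shifts

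*Combined protocol and SAP*

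**What the plan says.** In the section 3.5 table, the Aim 2 row defines its variables as "Using the VAS score from the enteral infusions and for hormones, the AUC values" and its analysis as "Spearman correlations between the VAS score and the AUC values for the various hormones, overall and separately by group (FD,DM, controls". It gives no arm stratum, arm covariate or restriction to one arm, and no other section supplies one.

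The two rows above do name the arm. The Aim 1 row will "compare VAS scores in response to lipid infusion + exendin vs. lipid infusion + placebo separately for each group". The row on ongoing symptoms lists "Potential predictor variables = VAS score during enteral lipid + placebo infusion, gastric emptying, age, gender, BMI".

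On allocation, the Abstract says that "subjects in each group (ie, healthy subjects, functional dyspepsia and DM) will be randomized to lipid infusion and placebo or lipid infusion" with exendin, 1:1. The parenthesis in section 3.3 (v) lists only the two patient groups, but the sample-size table also splits the controls, 12 against 12, alongside 20 against 20 in each patient group.

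On direction, Aim 2 in section 1 hypothesises that chemosensitivity is "associated with higher plasma CCK and GLP-1 concentrations B) reduced by the GLP-1 antagonist exendin 9-39".

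On the analytes, section 3.3 (v) states that "Plasma glucose, insulin, C-peptide, GLP-1, CCK, ghrelin, and PYY will be collected at 5 minute intervals" at first and at longer intervals later. Section 3.3 (vi) says the exendin dose has been shown to "block the effects of GLP-1 infused at supraphysiologic doses and the effects of endogenous GLP-1 on gastrointestinal motility and insulin secretion". It allows that some GLP-1 action on insulin secretion may persist but considers it probably small. It also reports mean glucose 6 mg/dl higher in healthy subjects and 19 mg/dl higher in type 2 diabetes after a duodenal meal.

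The last row of the table correlates permeability and tight-junction proteins with VAS, again without mention of arm.

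**The concern.** Read as written, exendin and placebo subjects enter one correlation. If exendin lowers VAS as Aim 2B proposes, the arm difference becomes part of the VAS spread, with three possible consequences.

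- A hormone that exendin does not shift has its within-arm correlation attenuated, and power falls.
- An analyte that exendin does shift becomes correlated with VAS through arm alone. A significant result would then partly restate the drug effect on VAS.
- For GLP-1, blocking the receptor may weaken the link in half the subjects, so a pooled estimate averages two different relationships.

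Aim 2A is a stated hypothesis, and this row is its only planned test. A null result for CCK or GLP-1 could partly reflect unmodelled arm differences.

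In the permeability row only the first consequence arises. The sugar test is scheduled on the morning before the infusion, and no exendin effect is reported on the biopsies taken on a later study day.

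**Working it through.** **1. The plan's own figure.** For 10% against 50% severe symptoms, 20 per arm, two-sided alpha 0.05:
- Pooled proportion 0.30; null SE = √(0.30 × 0.70 × 2/20) = 0.1449.
- Alternative SE = √(0.10 × 0.90/20 + 0.50 × 0.50/20) = 0.1304.
- z = (0.40 − 1.96 × 0.1449)/0.1304 = 0.89, so power is 81%.

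This matches the stated figure of about 80%. It concerns the randomised comparison; the plan gives no power for the Aim 2 correlations.

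**2. Range of VAS effects (assumptions).** The plan states no expected VAS effect in SD units. On a normal scale, 10% against 50% is 1.28 − 0 = 1.28 SD, and 10% against 68% (controls) is 1.28 + 0.47 = 1.75 SD. These are detectable differences, not forecasts. The same table puts functional dyspepsia on exendin at 10%, 60% and 30% severe in different columns. Half and a quarter of 1.28 SD (0.64 and 0.32) were therefore tried as well.

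**3. Attenuation when the hormone is not shifted.** With 1:1 arms and a VAS shift of d within-arm SDs, the pooled correlation is ρ/√(1 + d²/4). For ρ = 0.3:
- d = 0.32: 0.3/√1.0256 = 0.296
- d = 0.64: 0.3/√1.1024 = 0.286
- d = 1.28: 0.3/√1.4096 = 0.253

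Simulated power (normal VAS and hormone, groups of 24/40/40, 1:1 arms, 10,000 replicates, ρ = 0.3 in both arms):

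| VAS shift | n=104, ignoring arm | n=104, adjusted | n=40, ignoring arm | n=40, adjusted |
|---|---|---|---|---|
| 0 | 84% | 83–84% | – | – |
| 0.32 SD | 83–84% | 83–84% | – | – |
| 0.64 SD | 80–81% | 83–84% | 40% | 41–42% |
| 1.28 SD | 69% | 83% | 31% | 42–43% |
| 1.75 SD controls, 1.28 SD patients | 65% | 82–83% | – | – |

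Ranges cover simulation error and whether group is also adjusted for in the overall analysis. A placebo-only analysis has 53–54% power at n = 52.

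**4. Analytes that exendin shifts.** With no within-arm link and an analyte shift of h SDs in the same direction as VAS, the pooled correlation is (dh/4)/√[(1 + d²/4)(1 + h²/4)]. At d = 0.64:
- h = 0.25: 0.04/√(1.1024 × 1.0156) = 0.038
- h = 0.5: 0.08/√(1.1024 × 1.0625) = 0.074
- h = 1: 0.16/√(1.1024 × 1.25) = 0.136

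Simulated rejection rates at n = 104, nominal 5%:

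| VAS shift | h = 0.25 | h = 0.5 | h = 1 |
|---|---|---|---|
| 0.32 SD | 6% | 6% | 11% |
| 0.64 SD | about 6% | 12% | 28% |
| 1.28 SD | 10% | 27% | 73% |

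Adjusted for arm, the rate is about 5% throughout. If exendin raises the analyte, as with glucose, the rates are similar and the spurious correlation is negative. The values of h are assumptions; the documents give mean glucose differences without an SD.

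**5. Dilution of a GLP-1 link.** Assume ρ = 0.5 on placebo, a VAS shift of 1.28 SD and n = 104:

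| Share of link kept on exendin | Ignoring arm | Adjusted for arm | Placebo only |
|---|---|---|---|
| 0% | 53% | 67% | 95% |
| 25% | 72% | 86% | 95% |
| 50% | 87% | 96% | 95% |
| 75% | 96% | 99% | 95% |
| 100% | 99% | 100% | 95% |

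Placebo-only overtakes the adjusted analysis once roughly 55–60% of the link is lost.

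**The case against.** The strongest reply is that the row is silent rather than wrong. These are association analyses in a short table, no stated figure is contradicted, and any harm depends on effects the documents do not quantify. Much of this stands. At 0.64 SD the power loss is only a few points, and at 0.32 SD there is essentially none.

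It could also be said that placebo-only is implied. The row does not say so, and the row above shows how the plan writes that restriction. If it was intended, power at ρ = 0.3 would be 53–54% rather than about 83%.

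Several stronger readings are tempting, but the documents do not support them:

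- **That the CCK and GLP-1 correlations face inflated false positives.** No exendin shift is reported for either. Inflation is confined to glucose and plausibly insulin and C-peptide. The glucose rise is called modest, followed a duodenal meal rather than lipid, and lipid was chosen here to limit the effect on glucose. For insulin and C-peptide even the net direction is open: lost GLP-1 action would lower insulin, while higher glucose may raise it.
- **That the plan expects a VAS fall of 1.28 SD or more.** Those figures come from detectable differences. Only the direction is hypothesised, in Aim 2B.
- **That exendin abolishes the GLP-1–symptom link, so only placebo subjects are informative.** Section 3.3 (vi) suggests near-complete blockade for insulin secretion and also mentions motility. It does not address symptoms.
- **That group must also be adjusted for.** Sections 1 and 2 tie higher GLP-1 to increased sensitivity in functional dyspepsia, so between-group variation may be part of the question.

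**Conclusion.** The omission is real and worth correcting, but its size is conditional. For the two hormones in Aim 2A the documented risk is lost power: essentially none at a VAS shift of 0.32 SD or less, about 2–4 points at 0.64 SD, and about 15 points at 1.28 SD. This assumes ρ = 0.3 in both arms, normal variables and 104 completers. A GLP-1 link may be diluted further by an amount the documents do not fix. For glucose, insulin and C-peptide, false-positive rates at a VAS shift of 0.64 SD would be about 6%, 12% and 28% for assumed analyte shifts of 0.25, 0.5 and 1 SD. Here a false positive means rejection when there is no association within arms. The randomised comparison of exendin with placebo (Aim 2B) is not affected. Because adjustment costs almost nothing, it should be made even though the effect may prove small.

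**What to change.** In the Aim 2 row, replace plain Spearman with partial (rank) correlations adjusted for randomised arm, both overall and within each group. Adjust the VAS correlations with permeability and tight-junction proteins for arm in the same way. Adjustment for group in the overall analysis can be an optional sensitivity analysis.

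For GLP-1, report the placebo-arm and exendin-arm correlations with confidence intervals next to the arm-adjusted estimate. Give the placebo-arm estimate equal standing, because it is the more powerful once roughly 55–60% or more of the link is blocked. Do not make this reporting depend on an interaction test. With ρ = 0.5 on placebo and a VAS shift of 1.28 SD, that test has 70% power if the link is abolished and 24% if it is halved.

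Placebo-arm results within a single group should be labelled exploratory. By Fisher's z, the correlation detectable with 80% power is tanh[(1.96 + 0.84)/√(n − 3)], which is 0.38 at n = 52, 0.59 at n = 20 and 0.73 at n = 12.

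The cost is revised wording, a few lines of code and a few more reported estimates, with no new data. The arm term uses one degree of freedom, about one point of power if exendin does not change VAS.
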